SURGERY WITH OR WITHOUT STEROTACTIC BODY RADIOTHERAPY

A Prospective Randomized Phase II Study of Surgery with or without Adjuvant Stereotactic Body Radiotherapy (SBRT) in Patients with Previously-Irradiated Head and Neck Cancer

(Version Dated 2020-04-29)

Principal Investigator:

[name], PhD
UPMC Cancer Center
Mary Hillman Jennings Radiation Oncology Center
[name]
[name]
[name]
[contact]
Ph: [contact]
[contact]

Study Co-Investigators:

Radiation Oncology

[name] ([contact])
[name], PhD ([contact])
[name] ([contact])

Hematology Oncology

[name] [name] ([contact])

Otolaryngology

[name] [name] ([contact])
[name] ([contact])
[name] ([contact])
[name] ([contact])

Biostatistics

[name] ([contact])

TABLE OF CONTENTS

PROTOCOL SUMMARY	3
1.0 BACKGROUND	5
2.0 OBJECTIVES	7
3.0 INVESTIGATIONAL PLAN.....	8
4.0 SUBJECT SELECTION AND ELIGIBILITY.....	11
5.0 TREATMENT EVALUATION, ADMINISTRATION, AND MODIFICATION...	13
6.0 STATISTICAL CONSIDERATIONS.....	14
7.0 DATA SAFETY AND MONITORING.....	16
8.0 REFERENCES	17

PROTOCOL SUMMARY

Title

A Prospective Randomized Phase II Study of Surgery with or without Adjuvant Stereotactic Body Radiotherapy (SBRT) in Patients with Previously-Irradiated Head and Neck Cancer

Objectives

The *primary* objective of this study is to compare the 1-year local control in patients with operable, recurrent previously-irradiated squamous cell head-and-neck cancers with or without adjuvant SBRT.

The *secondary* objectives of this study are:

1. To determine the locoregional progression-free survival (PFS), distant PFS, overall PFS (local + regional + distant), and overall survival (OS).
2. To evaluate the acute and late toxicities of adjuvant SBRT in the re-irradiation setting following salvage surgery.
3. To determine prognostic factors that may predict the likelihood of local failure, regional failure, or OS in this cohort to guide future management.
4. To compare the impact of adjuvant SBRT versus a wait-and-see approach on patient reported quality of life (PR-QoL).
5. To compare surgical versus SBRT-induced immunological serum markers in relation to local control.

Patient population

In order to be eligible for this study, patients must have a pathologically proven recurrent or second-primary head-and-neck cancer with no evidence of distant metastases. Patients must be at least 18 years of age and able to give informed consent. They must have a Karnofsky Performance Status ≥ 60 .

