Number of patients

42

Study design and methodology

This is a prospective, double-arm phase II study. The treatment schema detail is in Section 6.3.

Treatment administered

Patients will or will not receive adjuvant Stereotactic Body Radiotherapy (SBRT) at various levels depending upon tumor volume. Subsequent evaluations will measure the efficacy of the adjuvant SBRT.

Efficacy data collected

The following evaluations will be performed to assess the efficacy of preoperative stereotactic radiation therapy:

- Objective local control rate measuring tumor volume
- Health Related Quality of Life assessment using the University of Washington Quality-of-Life-Revised (UW-Qol-R)

Safety data collected

The following evaluations will be conducted to assess the safety of radiosurgery:

- Recording of all toxicity data per NCI CTCAE version 4.0

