3.6.4 Follow-up/Long-term follow-up/Extended long-term follow-up procedures

Follow-up evaluations will be completed in patients in both arms (SBRT and wait-and see). They will be carefully followed every 3-6 months for 24 months or until death. Evaluations will consist of the following:

- Interim medical history and physical examination
- Careful documentation of Toxicity According to National Cancer Institute Common Toxicity Criteria Events Scale version 4.0
- Follow-up Patient-Reported Quality of Life Assessment (PR-QoL)
- FDG PET-CT at 8-12 weeks post-treatment then every 12 weeks

TABLE 1: Treatment Schema

		Clinical Visit			
Assessment		Pre-Study	During 8-12 weeks	Q 12-24 weeks	SBRT Post for 2-years
	History + Physical	X	X	X	X
	Imaging	X	X	X	
	QoL Assessment	X	X	X	

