6.0 STATISTICAL CONSIDERATIONS

6.1 Study objectives and design

The primary objective is to compare the 1-year local control in patients with operable, recurrent previously-irradiated squamous cell head-and-neck cancers with or without adjuvant SBRT.

Secondary objectives include to determine the locoregional progression-free survival (PFS) distant PFS, overall PFS (local + regional + distant), and overall survival (OS); to evaluate the acute and late toxicities of adjuvant SBRT in the re-irradiation setting following salvage surgery; to determine prognostic factors that may predict the likelihood of local failure, regional failure, or OS in this cohort to guide future management; and to compare the impact of adjuvant SBRT versus a wait-and-see approach on patient reported quality of life (PR-QoL),

This clinical trial is planned as a prospective, randomized, two-arm Phase II study.

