6.3 Statistical approach and analysis

(1) Efficacy Analysis Set: includes all enrolled and randomized patients. Subjects will be analyzed according to their randomized treatment group assignment.

(2) Safety Analysis Set: The safety analysis will be performed according to the actual treatment received.

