6.4 Analysis of primary and secondary endpoints

Survival endpoints will be estimated by the Kaplan-Meier method and the corresponding median survival times (with 95% confidence interval) reported. The one-year LPFS will also be estimated along with its 95% confidence interval. Survival will be compared between the two arms with the one-sided log-rank test. Effect of treatment and other variables (e.g., baseline characteristics, biomarkers etc) on survival will be explored with Cox regression models.

For the quality of life (QoL) data analysis, each item of the UW-QoL-R will be individually assessed. The mean and standard deviation of the observed data will be summarized at each collection time and plotted against time, from baseline through the end of patient follow-up. Generalized linear models (such as cumulative logit models) for repeated measures will be used to explore if there are significant changes in PR-QOL over time.

Using NCI Common Terminology Criteria for Adverse Events (CTCAE v4.0), the number of patients experiencing adverse events over their course of treatment will be characterized by type of adverse event and grade, by the time of onset in relation to the first day of therapy, and whether the event is clinically significant. Attribution of adverse events to treatment (unrelated, unlikely, possibly, probably, or definitely) will also be summarized for any serious adverse events (SAEs), CTCAE grade 3 or higher. The percentage of patients experiencing SAEs that are considered to be treatment-related (probable or definite) will be determined. The percentages of patients experiencing the acute/late toxicities associated with SBRT will also be estimated along with their exact 95% confidence intervals.

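### Objective 2.5 asks for an SBRT versus wait-and-see comparison of quality of life, but the only QoL inference stated in section 6.4 is change over time

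*Combined protocol and SAP*

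**What the plan says.** The QoL objective is comparative wherever it appears. Secondary objective 4 of the Protocol Summary and objective 2.5 in section 2.0 both read "To compare the impact of adjuvant SBRT versus a wait-and-see approach on patient reported quality of life (PR-QoL". Section 6.1, inside the statistics chapter, repeats it: "to compare the impact of adjuvant SBRT versus a wait-and-see approach on patient reported quality of life (PR-QoL".

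Section 6.4 covers the QoL analysis in three sentences. First, "each item of the UW-QoL-R will be individually assessed". Second, means and standard deviations of the observed data are given at each collection time and plotted; the text does not say by arm. Third, generalized linear models for repeated measures, with cumulative logit models as the example, "will be used to explore if there are significant changes in PR-QOL over time".

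For survival the same section is explicit: "Survival will be compared between the two arms with the one-sided log-rank test". It then adds Cox models for the effect of treatment and other variables on survival.

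Three other places bear on the point:
- The Protocol Summary lists this among the efficacy data: "Health Related Quality of Life assessment using the University of Washington Quality-of-Life-Revised (UW-Qol-R".
- Section 6.3 says of the efficacy set: "Subjects will be analyzed according to their randomized treatment group assignment".
- Section 3.6.4, which includes the QoL assessment, says: "Follow-up evaluations will be completed in patients in both arms (SBRT and wait-and see".

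**The concern.** A model of change over time estimates a different quantity from the one objective 2.5 names. A statistician who followed section 6.4 to the letter could complete the QoL analysis and still have no estimate of how SBRT compares with wait-and-see.

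An arm comparison could be added later, but its form would then be chosen with the data in view. An arm main effect, an arm-by-visit interaction and a difference at one visit are three different quantities. There are also several items and several visits to choose from.

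QoL matters to the reading of this trial. Section 1.2 cites grade 3 or 4 late toxicity of 39% versus 10% with an earlier adjuvant chemotherapy and re-irradiation regimen. Whether any gain in local control comes at a cost to the patient is therefore a question the trial will be expected to address.

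**Working it through.** **1. The passages side by side.**

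| Place | What it fixes for QoL | Between-arm QoL estimate or test? |
|---|---|---|
| Protocol Summary, 2.5, 6.1 | The question: SBRT versus wait-and-see | It is the question, not an analysis |
| Protocol Summary, efficacy data | UW-QoL-R counts as efficacy data | No |
| 6.3 | Efficacy set grouped as randomised | No |
| 6.4, survival text | Log-rank between arms; Cox with treatment effect | No, both are tied to survival |
| 6.4, QoL text | Item-level summaries; models of change over time | No |

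Section 6.4 thus states two between-arm analyses for survival and none for QoL.

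**2. Why a time effect is not a substitute.** Let dS and dW be the mean changes from baseline in the SBRT and wait-and-see arms, in SD units, with equal arm sizes.

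- Average change over time = (dS + dW)/2
- Arm difference = dS - dW

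Case A, both fall by 0.5: average = (-0.5 - 0.5)/2 = -0.5; difference = -0.5 - (-0.5) = 0.

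Case B, one rises and one falls by 0.5: average = (0.5 - 0.5)/2 = 0; difference = 0.5 - (-0.5) = 1.0.

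Case A would readily be significant. With 42 patients, complete data and an assumed correlation of 0.5 between baseline and follow-up, the SD of change is sqrt(2 x (1 - 0.5)) = 1.0 SD. The standard error is 1/sqrt(42) = 0.154 SD, and z = -0.5/0.154 = -3.2. So the time effect can be significant with no arm difference, and zero with a large one. The cases show the principle and are not forecasts.

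**3. The precision the missing contrast would have.** The documents give no QoL sample size, power or alpha. The 21 per arm in section 6.2 is set by LPFS, and it reproduces:

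- HR = ln(0.52)/ln(0.20) = 0.406
- Events (Schoenfeld, one-sided 0.10, 90% power) = 4 x (1.2816 + 1.2816)^2 / (ln 0.406)^2 = 32.4, so 33
- With exponential LPFS, two years' uniform accrual and one further year, the mean event probability is 0.825 with no loss and 0.799 with 5% loss a year
- Patients per arm = 33/0.825/2 = 20.0, or 33/0.799/2 = 20.7, so 21

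For one item treated as continuous at one visit, in SD units:

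- 95% CI half-width, unadjusted = 1.96 x sqrt(1/21 + 1/21) = 1.96 x 0.3086 = 0.605
- Baseline-adjusted = 0.605 x sqrt(1 - r^2). With r = 0.5 (assumed): 0.605 x 0.866 = 0.524. For r from 0.3 to 0.7: 0.577 to 0.432

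With t quantiles in place of 1.96, the first two become 2.021 x 0.3086 = 0.624 and 2.023 x 0.3086 x 0.866 = 0.541. Rounded, they remain about 0.6 and 0.5 SD.

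The documents do not say how many patients will have QoL data. If, as an assumption, 15 or 10 per arm have data at the chosen visit, the unadjusted half-widths with t quantiles are 2.048 x sqrt(2/15) = 0.75 SD and 2.101 x sqrt(2/10) = 0.94 SD.

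**The case against.** The strongest reply is that the comparison is implied. QoL is efficacy data, the efficacy set is analysed as randomised, both arms are assessed, and section 6.1 restates the comparison in the statistics chapter. The model family is given by example only and can carry an arm term, and most statisticians would include one. This stands in part: grouping by arm is strongly implied, and asking for summaries by arm is largely clarification. It does not supply the contrast. Section 6.3 says which arm a patient is counted in; it does not say which difference is estimated, or at which visit. A reader might go further and infer that the plan rules out an arm comparison of QoL. It does not: nothing excludes an arm term.

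A second reply is that this is an exploratory secondary analysis in a 42-patient phase II trial, and that the LPFS conclusion does not depend on it. That is right. It limits the weight of the point and favours estimation over testing, but it does not turn a time effect into an answer to objective 2.5.

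A reader might also infer from the assumed one-year LPFS of 20% versus 52% that QoL forms will be available in about those proportions. The documents do not support this. Section 3.6.4 follows patients for 24 months or until death, and nothing stops QoL collection at local progression. LPFS combines local progression with death (section 5.1), and no survival rate is assumed. Deaths and missing forms will reduce the numbers, but how far, and how unequally, cannot be derived from the plan.

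Finally, an ordinal model with arm-by-visit terms, fitted item by item with at most 21 per arm, may meet sparse response levels and fail to converge. That is a fair criticism of any remedy, so a fallback should be specified.

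**Conclusion.** The point holds as a mismatch between objective and analysis: the comparison named in objective 2.5 has no stated analysis, and the inference that is stated targets another quantity. This rests on the text of sections 2.0, 6.1, 6.3 and 6.4 and on no numerical assumption.

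The point should be corrected, but it does not threaten the trial's primary conclusion. Specifying the contrast will not make it precise. The half-widths of about 0.6 SD (unadjusted) and 0.5 SD (baseline correlation 0.5) assume 21 per arm, complete data and an item treated as continuous. Deaths or missing forms widen them. An interval that includes zero could not be read as equal QoL in the two arms.

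**What to change.** In section 6.4:

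- Keep the item-by-item repeated-measures models, but include randomised arm, visit, arm-by-visit and baseline score. Summarise and plot each item by arm.
- For each item, report the SBRT versus wait-and-see difference with its 95% CI at one visit window named in advance and timed from randomisation. Present this as estimation, for all items, without selecting any by significance. Label other visits exploratory.
- Name a simpler fallback, such as a baseline-adjusted mean difference, for use if the ordinal model does not converge because of sparse levels.
- Report the number with QoL data and the number of deaths by arm and visit, and state that the result applies to patients alive at that visit.

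The cost is mainly wording. The questionnaire is already planned in both arms, so no patients or procedures are added. The timing needs care. Section 3.5 counts follow-up from treatment, and the wait-and-see arm has no SBRT date. Visits are also 3 to 6 months apart, so the window must be defined to suit, and section 3.6.4 may need a line to match. The drawback is the limited precision shown above, which should be stated alongside the result.

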5.0 TREATMENT EVALUATION, ADMINISTRATION, AND MODIFICATION

5.1 Primary outcome variables to be evaluated

- (1) Primary endpoint - local progression-free survival (LPFS), defined as the time from the date of randomization to the date of local progression or the date of death from any cause. Subjects who are alive and have not progressed will be censored at their last follow-up date.
- (2) Regional PFS, distant PFS, PFS (local + regional + distant): The definition of these endpoints is similar to LPFS.
- (3) Overall Survival: time from the date of randomization to the date of death due to any cause.
- (4) Acute and late toxicities of adjuvant SBRT. Acute toxicity is defined as toxicity occurring within 3 months of completion of SBRT. Late toxicity is defined as toxicity occurring later than 3 months after SBRT treatment.

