7.2 Adverse events

All serious AE shall be reported meeting criteria for reporting can be found on the University of Pittsburgh Institutional Review Board's website at <http://www.irb.pitt.edu>. In the event of such adverse event, the investigator must report the event(s) via phone within 24 hours and a written report filed within 24 hours to the Principal Investigator, or the University of Pittsburgh Cancer Institute's Department of Radiation Oncology's Protocol Office.

All adverse events will be reported as per the University of Pittsburgh IRB web site at www.irb.pitt.edu .

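### The treatment-related SAE percentage leaves out events rated possibly related, and no attribution-free grade 3 or higher percentage by arm is planned beside it

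*Combined protocol and SAP*

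**What the plan says.** Section 6.4 plans four safety summaries.

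- A table of all events: "the number of patients experiencing adverse events over their course of treatment will be characterized by type of adverse event and grade". Onset is timed from the first day of therapy.
- A five-level attribution summary: "Attribution of adverse events to treatment (unrelated, unlikely, possibly, probably, or definitely) will also be summarized". It is limited to "any serious adverse events (SAEs), CTCAE grade 3 or higher".
- A related-event percentage: "The percentage of patients experiencing SAEs that are considered to be treatment-related (probable or definite) will be determined". No confidence interval is mentioned for it.
- Acute and late toxicity: "The percentages of patients experiencing the acute/late toxicities associated with SBRT will also be estimated along with their exact 95% confidence intervals".

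Section 5.1 defines acute and late by time alone: "Acute toxicity is defined as toxicity occurring within 3 months of completion of SBRT", and late toxicity is whatever occurs after that window. Both windows are counted from SBRT.

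On serious events, section 7.2 says: "All serious AE shall be reported meeting criteria for reporting can be found on the University of Pittsburgh Institutional Review Board's website". The protocol itself lists no seriousness criteria.

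Three other places bear on the point. Section 3.5 gives the second arm no SBRT, and neither a sham nor blinding is described anywhere. Section 3.6.4 has toxicity documented at follow-up in both arms. Section 6.3 analyses safety by treatment actually received.

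**The concern.** Attribution is hard in this population. Section 4.3 requires earlier radiotherapy of at least 50 Gy and salvage surgery, and it allows concurrent or adjuvant systemic therapy. Section 3.6.3.2 has SBRT completed within 4 to 12 weeks of that surgery. A local event after SBRT therefore often has another plausible cause, and *possibly* is a natural rating for it. The related-event percentage does not count that rating.

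Toxicity of adjuvant SBRT is a secondary objective (2.3), and less toxicity than conventional adjuvant re-irradiation is part of the rationale (1.4). The benchmark in section 1.2, 39% against 10% with grade 3 or 4 late toxicity in the cited phase III trial, is given with no attribution filter stated. If a probable-or-definite percentage were set beside it, unlike quantities would be compared. A percentage by randomized arm that ignores attribution would avoid the problem, but the plan does not ask for one. The primary endpoint and the sample size are not involved.

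**Working it through.** **Denominator.** The plan states no expected toxicity rate, so there is no toxicity figure to reproduce. The only planning number used here is 21 patients per arm (section 6.2), and it reproduces. Under exponential survival the hazard ratio is ln(0.52)/ln(0.20) = 0.406. The Schoenfeld formula with one-sided alpha 0.10 and 90% power gives 33 events. With two years of accrual, one further year of follow-up and 5% annual loss (my reading of the stated loss), the mean event probability is 0.799, and 33/(2 × 0.799) = 20.7, or 21 per arm.

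**Direction.** Let A be the patients with at least one SAE rated possibly, probably or definitely related, and B those with at least one rated probably or definitely. B is contained in A, so B/n ≤ A/n always. This needs no assumption.

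**Size.** Let s be the share of patients in A whose highest rating is *possibly*. Then the planned percentage = (1 − s) × the inclusive percentage. The documents give neither s nor the inclusive rate, so both are assumed. The 39% is borrowed from section 1.2 and belongs to a different regimen.

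| Inclusive rate | s = 25% | s = 50% | s = 75% |
|---|---|---|---|
| 39% | 29% | 20% | 10% |
| 20% | 15% | 10% | 5% |

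In whole patients, 39% of 21 is about 8. The exact (Clopper-Pearson) 95% intervals are:

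- inclusive, 8/21 = 38% (18% to 62%);
- 3 of the 8 *possibly* only: 5/21 = 24% (8% to 47%);
- 4 of the 8 *possibly* only: 4/21 = 19% (5% to 42%).

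**Does another planned summary give an attribution-free comparison by arm?**

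| Summary in 6.4 | Free of attribution? | Covers late events? | Usable in the no-SBRT arm? |
|---|---|---|---|
| By type and grade | Yes | Not if the course of treatment is read literally | No defined first day of therapy |
| Five-level attribution, SAEs | No, but all levels shown | Not restricted | Attribution to SBRT has little meaning |
| Related percentage | No | Not restricted | Same |
| Acute and late percentages | Unclear: no cut-off for association with SBRT | Yes | Windows counted from SBRT |

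SBRT takes 1 to 2 weeks (sections 3.5 and 3.6.3), while late toxicity starts more than 3 months after it (section 5.1). A table confined to the course of treatment therefore cannot contain late events. None of the four is specified as an all-cause grade 3 or higher percentage by arm over follow-up.

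**Seriousness and grade.** The phrase in 6.4 has two readings. The illustration above does not depend on which is meant.

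- *As a definition* (an SAE is any grade 3 or higher event), it drops serious events of grade 1 or 2 and adds grade 3 events that are not serious. The two act in opposite directions, so the net effect is unknown.
- *As a restriction* (SAEs that are also grade 3 or higher), it can only lower the count.

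Both assume that the criteria cited in 7.2 do not coincide with grade 3 or higher. The documents do not reproduce those criteria.

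**The case against.** The best defence is that the percentage is openly labelled as probable or definite, and where to cut an attribution scale is a convention. If most local events have competing causes, counting *possibly* could overstate the harm of SBRT just as leaving it out could understate it. Knowing the arm could also push ratings up as well as down. All of this stands: the inclusive rate is not the true rate, and no bias in a known direction against the truth has been shown.

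A reader might also infer that this percentage is the headline toxicity figure and that *possibly* related events are lost. The documents support neither. Section 6.4 does not rank its safety summaries, and the only ones given confidence intervals are the acute and late percentages, which match objective 2.3 more closely. All five attribution levels are summarised for the same SAEs, so the *possibly* rated ones remain visible.

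The defence does not supply the missing comparison. The five-level summary leaves the stated percentage as it is, the table by type and grade is limited in time, and the acute and late percentages do not say what counts as associated with SBRT.

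**Conclusion.** The point holds as a minor one. It is certain that the planned related percentage is at or below the one that includes *possibly* rated events, and that no all-cause grade 3 or higher percentage by arm over follow-up is specified. That attribution is made knowing the arm is an inference from the absence of any described sham or blinding.

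The size is not known. Under assumed inclusive rates of 20% to 39% and assumed *possibly*-only shares of 25% to 75%, the planned figure would lie between 5% and 29%. The 24% against 38% contrast is illustrative only: the 3-of-8 split is invented, and with 21 patients both intervals are wide.

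It is tempting to conclude that equating SAEs with grade 3 or higher also understates harm. That does not follow, because under that reading the errors run both ways. What can be said is that two analysts could build different numerators from the same sentence.

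**What to change.** In section 6.4:

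1. Report the percentage of patients with SAEs possibly, probably or definitely related to treatment, with an exact 95% confidence interval, and keep the probable-or-definite percentage beside it.
2. Add the percentage of patients with any grade 3 or higher event, regardless of attribution, by arm and over the whole follow-up, counted from a date that exists in both arms, such as randomization.
3. Tabulate grade 3 or higher events and SAEs separately, and use the term SAE only for events meeting the criteria that section 7.2 refers to.

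Items 1 and 2 use attribution ratings the plan already calls for and toxicity data already to be collected in both arms under section 3.6.4, so they need only a wording change. Item 3 may need a seriousness field on the data form if there is none. The other cost is that the stated related percentage becomes less favourable wherever *possibly* is used. Sample size and efficacy analysis do not change.

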3.5 Timeline of study procedures

Once eligible by screening and enrolled in study, patients will be randomized into one of two arms. One arm will receive SBRT treatment for 1 – 2 weeks. The second arm will receive no SBRT and will continue with standard of care treatment. Patients will be followed for 8-12 weeks after treatment and every 3-6 months for up to 24 additional months. Extended long-term follow-up will occur as clinically indicated until death.

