6.2 Sample size and accrual rate

Forty (40) patients will be screened for each arm of the trial so that 21 subjects will be cleared to participate in research procedures in each arm of the trial.

The following assumptions are used in determining the sample size for this study:

Primary endpoint: local progression-free survival (LPFS)

One-sided type I error rate: 0.10

Statistical power: 90%

One-year LPFS for surgery alone: 20%

One-year LPFS for surgery + SBRT: 52%

Randomization: 1:1

2-year accrual period and one year follow-up following closure of accrual

5% lost to follow-up in each arm

To have 90% power to detect the above 32% difference in one-year LPFS, using a onesided log-rank test with a 0.1 level of significance, 21 patients are required in each arm.

The randomization of subjects to one of the two treatment arms will be in a 1:1 ratio. The UPCI Biostatistics Facility has a randomizer, an intranet application for randomly assigning patients to different treatments, which will be used for the randomization in this trial.

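### Late toxicity is planned as a crude percentage with no time horizon, although follow-up will differ between patients; a cumulative incidence at fixed times is a cheap, minor improvement

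*Combined protocol and SAP*

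**What the plan says.** Section 6.4 gives one method for both kinds of toxicity: "The percentages of patients experiencing the acute/late toxicities associated with SBRT will also be estimated along with their exact 95% confidence intervals". Section 5.1 separates them. For acute toxicity, "Acute toxicity is defined as toxicity occurring within 3 months of completion of SBRT". For late toxicity, "Late toxicity is defined as toxicity occurring later than 3 months after SBRT treatment". The acute window is closed; the late window has a start and no end.

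Three passages bear on how long patients are observed:
- Section 6.2, among the sample size assumptions: "2-year accrual period and one year follow-up following closure of accrual" and "5% lost to follow-up in each arm".
- Section 3.6.4, on visits in both arms: "They will be carefully followed every 3-6 months for 24 months or until death".
- Section 3.5, beyond that: "Extended long-term follow-up will occur as clinically indicated until death".

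Section 6.3 says that safety is analysed by treatment received. No section gives a date or time point for the late rate, the number at risk to go with it, or a rule for patients lost or still under observation. Kaplan-Meier estimation in section 6.4 is for survival endpoints only. That section also describes adverse events by time of onset, which is a description and not an incidence estimate.

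**The concern.** An exact binomial interval suits acute toxicity, because the window is short and the same for everyone treated. Late toxicity is different. At the cut-off implied by section 6.2, the last patient enrolled has one year of potential follow-up and the first has three. If all SBRT patients form the denominator, which is the natural reading, a patient observed for one year without an event weighs the same as one observed for two.

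The interval is valid for the quantity it estimates, but that quantity is an average risk over whatever follow-up happened to accrue. A reader may take it as a 1-year or a 2-year risk, and the error has opposite signs in the two cases. Evaluating late toxicity is a secondary objective (section 2.3), and section 1.4 presents lower toxicity than conventional adjuvant radiotherapy as part of the rationale for SBRT. A late rate used in that argument needs a stated horizon.

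**Working it through.** **The plan's own figure.** The documents give no figure for late toxicity, but the follow-up assumption can be checked through the sample size. With exponential LPFS, HR = ln(0.52)/ln(0.20) = 0.406. Schoenfeld's formula at one-sided 0.10 and 90% power gives 33 events. Uniform accrual over 2 years plus 1 year gives event probabilities of 0.940 and 0.710, mean 0.825, so 33/0.825 = 40 patients, or 20 per arm. With 5% loss per year this is 20.7, so 21. The plan's 21 per arm is reproduced, and 1 to 3 years of potential follow-up is what the design assumes.

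**Expected crude rate against incidence at a fixed time.** Assumptions not in the documents:
- constant death hazard m of 0.3, 0.5 or 0.7 per year from randomization;
- constant late toxicity hazard h of 0.3 or 0.5 per year, starting at s = 0.35 years;
- follow-up uniform on 1 to 3 years, capped at 2.25 years (about 24 months after the first post-treatment visit);
- 5% of patients lost, at a uniform time within their own follow-up.

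The cumulative incidence with death competing is

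F(t) = e^(-ms) × h/(h+m) × [1 - e^(-(h+m)(t-s))].

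For h = m = 0.5, e^(-0.175) × 0.5 = 0.4197. Then:
- 1 year: 0.4197 × (1 - e^(-0.65)) = 0.201.
- 2 years: 0.4197 × (1 - e^(-1.65)) = 0.339.
- Crude rate without loss: the mean of F over the follow-up distribution. F(2.25) = 0.357, and the integral of F from 1 to 2.25 is 0.368, so (0.368 + 0.75 × 0.357)/2 = 0.318.
- Crude rate with 5% loss, by simulation: 0.310 to 0.311.

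All six combinations (crude with 5% loss; the last column is the difference from the 2-year value times 21):

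| m | h | Crude | 1-year | 2-year | Crude / 2-year | Gap, patients |
|---|---|---|---|---|---|---|
| 0.3 | 0.3 | 25.5% | 14.5% | 28.3% | 0.90 | 0.6 |
| 0.3 | 0.5 | 37.5% | 22.8% | 41.2% | 0.91 | 0.8 |
| 0.5 | 0.3 | 20.9% | 12.8% | 23.1% | 0.91 | 0.4 |
| 0.5 | 0.5 | 31.0% | 20.1% | 33.9% | 0.92 | 0.6 |
| 0.7 | 0.3 | 17.4% | 11.2% | 19.0% | 0.92 | 0.3 |
| 0.7 | 0.5 | 25.9% | 17.7% | 28.1% | 0.92 | 0.5 |

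The crude rate is 8-10% (relative) below the 2-year value and far above the 1-year value in every row.

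**Sensitivity.** A second set of assumptions starts late toxicity at 3 months, stops collection at 24 months and takes loss as 5% per year. Late toxicity at 24 months without deaths is 10%, 20% or 39% (the last borrowed from the trial cited in section 1.2, for range only), and deaths make up 0 to 100% of the SBRT-arm LPFS hazard.
- The crude rate is 0.82 to 0.88 of the 24-month incidence at the design cut-off.
- With 39% and half the hazard being death: 12-month incidence 15.7%, 24-month 28.0%, crude 24.1%, Aalen-Johansen 27.9% on average (20,000 simulated trials of 21). The gap is 3.9 points, or 0.8 patients.
- The gap exceeds one patient only with 39% and a quarter or less of the hazard being death (32.9 - 28.0 = 4.9 points, 1.0 patient; with no deaths, 39.0 - 32.6 = 6.4 points, 1.3 patients).

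**If everyone is followed to 24 months or death.** Under the second set the ratio rises to 0.94-0.96, with loss the only remaining cause. Under the first set with h = m = 0.5 and everyone followed to 2.25 years apart from losses, crude is slightly above the 2-year value (34.7% against 33.9%).

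**Early deaths.** LPFS is "defined as the time from the date of randomization to the date of local progression or the date of death from any cause", so deaths cannot exceed LPFS events. If SBRT ends 0.04 to 0.19 years after randomization (assumed; not fixed by the documents), the late window opens at 0.29 to 0.44 years. The bound on deaths by then is 1 - 0.52^0.29 = 17% to 1 - 0.52^0.44 = 25%, or 3.6 to 5.3 of 21 patients. The actual number is unknown.

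**The case against.** A reader might infer that the planned rate understates late risk because many patients die before or during the late window. The documents do not support this. They give no overall survival or death rate, only composite LPFS, so the 17-25% is a ceiling on early deaths. A patient with local progression stays on the visit schedule and can still be assessed for toxicity. Death also does not bias a crude percentage as an estimate of cumulative incidence: Aalen-Johansen from SBRT completion keeps early deaths in the denominator without an event, exactly as the crude rate does. Deaths dilute the rate only relative to patients still at risk when the window opens (about 37% in the example with both hazards 0.5, against 31% crude), and neither estimator targets that quantity.

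Three further objections have force. First, the one-year period after accrual is a sample size assumption, not a stated toxicity cut-off; if toxicity is reported after all patients reach 24 months or die, the gap nearly vanishes. Second, the gap is small beside sampling error: 5/21 has an exact interval of 8.2% to 47.2%, and in the simulated trials such intervals covered the true 24-month value in 95.6% to 99.2% of runs. Third, late toxicity is descriptive, with no test or threshold attached, and section 6.4 already describes onset times.

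These points limit the size of the problem. They do not supply a horizon, and the plan does not commit to reporting only after complete 24-month follow-up.

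**Conclusion.** The point holds as a defect of definition. The planned late percentage refers to no stated time and treats censored patients as event-free. Its direction depends on the comparison: below the 2-year incidence at the design cut-off, above the 1-year incidence, and near the 2-year value with complete 24-month follow-up. It should therefore not be called downward-biased without naming a 2-year target and that cut-off.

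The 8-10% shortfall rests on assumed constant hazards and 5% total loss; with 5% loss per year and collection stopped at 24 months it is 12-18%. The upper death hazard of 0.7 is slightly beyond what the plan's LPFS allows (-ln 0.52 = 0.654). The expected change is under one patient of 21 over the main range, and 1.3 at the extreme of the wider one. Severity is minor; the case for acting is that the better estimator costs almost nothing.

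**What to change.** In section 6.4, keep percentages with exact 95% intervals for acute toxicity only. For late toxicity, state that the cumulative incidence will be estimated by Aalen-Johansen at 1 and 2 years from SBRT completion, with death as a competing event, patients censored at their last toxicity assessment, and a 95% confidence interval. Report the number alive and under follow-up at 3 months, so that readers can see how many patients entered the late window. State the data cut-off for this analysis.

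The cost is a few lines of SAP text and slightly more analysis, with no new patients. Onset times are already to be described; the date of the last toxicity assessment is also needed. Intervals will be wide. At the design cut-off only half the patients have 2 years of potential follow-up, so about 21 × 0.5 × e^(-0.6) = 5.8 to 21 × 0.5 × e^(-1.4) = 2.6 would be alive and observed at 2 years under death hazards of 0.3 to 0.7. The 2-year figure is therefore better reported once scheduled follow-up is complete.
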